Patients discontinued from the study prior to completion will be asked to return for an early termination visit after a minimum of 30 days have elapsed following the final study treatment for monitoring of adverse events and the early termination visit assessments. Early termination visits not completed after 6 months following the last treatment will be considered as "loss of follow-up" when appropriate.

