## 3.3.1 Rationale for FHTR2163 Dose and Schedule

To provide assessment of the relationship between dosing interval and efficacy, two FHTR2163 treatment arms will be evaluated in this Phase II study, a 20-mg dose administered ITV Q4W and a 20-mg dose administered ITV Q8W.

In the Phase I study (GR39821), 20 mg of FHTR2163 was the maximum dose tested and was administered ITV Q4W for three doses. The 20-mg dose and the Q4W interval were found to be well tolerated. The 20-mg dose administered Q4W allows evaluation of the highest exposure of FHTR2163.

The Q8W dosing regimen will be assessed to allow evaluation of a longer dosing interval, which is a major priority for patients, caregiver, and physicians in this disease indication. On the basis of the observed serum and aqueous PK data, estimated vitreal drug concentrations for a typical patient treated with 20 mg Q8W are maintained above the 50% inhibitory concentration of 3.58 nM established in a cynomolgus monkey PK/pharmacodynamic (PD) study (16-0265). In addition, the Q8W dosing interval is supported by the observed PD biomarker data from aqueous humor samples collected during the Phase I study (GR39821), which suggest inhibition of HtrA1 activity through at least 8 weeks following a 20-mg dose.

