# 4.6 TREATMENT, PATIENT, STUDY, AND SITE DISCONTINUATION

# 4.6.1 Study Treatment Discontinuation

Patients must permanently discontinue study treatment if they experience any of the following:

- Any medical condition that the investigator or Sponsor determines may jeopardize the patient's safety if he or she continues to receive study treatment
- Investigator or Sponsor determination that treatment discontinuation is in the best interest of the patient
- Pregnancy
- Unacceptable toxicity
- Any event that meets treatment discontinuation criteria defined in Table 1 in Section 5.1.5.

The primary reason for study treatment discontinuation should be documented on the appropriate eCRF.

Patients withdrawn from the study prior to completion will be asked to return for an early termination evaluation after a minimum of 30 days following his or her final study treatment for monitoring of adverse events and assessments listed for the early termination visit (see Appendix 1 and Appendix 2). The reason for the discontinuation should be recorded on the appropriate eCRF. Discontinued patients will not be replaced or allowed to re-enter the study.

Patients who discontinued treatment will not be allowed to re-start the study treatment. However, they should be strongly encouraged to stay in the study and undergo as many scheduled visits as possible.

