# 5.1.3 Risks Associated with Aqueous Humor Sampling through Anterior Chamber Paracentesis

Sampling of aqueous humor through anterior chamber paracentesis is a valuable procedure in providing samples for assessment of ocular PK and PD parameters of FHTR2163. Potential ocular safety issues may include cataract development or progression, anterior chamber hemorrhage, decreased IOP and/or hypotony, and decreased BCVA. There have also been rare reports of serious complications, including endophthalmitis and corneal abscess.

The procedure will be performed by experienced ophthalmologists familiar with aqueous humor sampling through anterior chamber paracentesis (see Appendix 14 for anterior chamber paracentesis and aqueous humor sampling procedures), and patients will be monitored closely for occurrence of any potential adverse event associated with the procedure.

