# 5.3.1 Adverse Event Reporting Period

Investigators will seek information on adverse events at each patient contact. All adverse events, whether reported by the patient or noted by study personnel, will be recorded in the patient's medical record and on the Adverse Event eCRF.

After informed consent has been obtained but prior to initiation of study drug, only serious adverse events caused by a protocol-mandated intervention (e.g., invasive procedures such as biopsies, discontinuation of medications) should be reported (see Section 5.4.2 for instructions for reporting serious adverse events).

After initiation of study drug, all adverse events will be reported until 28 days after the final dose of study drug. After the 28-day period, only serious adverse events (1) caused by a protocol-mandated intervention (e.g., invasive procedures such as aqueous humor sample), or (2) believed to be related to prior study drug treatment (see Section 5.6) should be reported (see Section 5.4.2 for instructions for reporting serious adverse events).

Instructions for reporting adverse events that occur after the adverse event reporting period are provided in Section 5.6.

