#### 5.4.2.2 Events That Occur after Study Drug Initiation

After initiation of study drug, serious adverse events, adverse events of special interest, should be reported within 24 hours after learning of the event until the final study visit (Week 76). Investigators should record all case details that can be gathered immediately (i.e., within 24 hours after learning of the event) on the Adverse Event eCRF and submit the report via the EDC system. A report will be generated and sent to Safety Risk Management by the EDC system.

In the event that the EDC system is unavailable, the paper Clinical Trial Serious Adverse Event/Adverse Event of Special Interest Reporting Form provided to investigators should be completed and submitted to the Sponsor or its designee immediately (i.e., no more than 24 hours after learning of the event), either by faxing or by scanning and emailing the form using the fax number or email address provided in Section 5.4.2.1. Once the EDC system is available, all information will need to be entered and submitted via the EDC system.

Instructions for reporting serious adverse events that occur after the final study visit (Week 76) are provided in Section 5.6.

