- aa After informed consent has been obtained but prior to initiation of study treatment, only serious adverse events caused by a protocol-mandated intervention should be reported. Adverse events will be recorded starting on Day 1 after the study treatment until 28 days after the final dose of study drug. After the 28 day period, only serious adverse events caused by a protocol-mandated intervention or believed to be related to prior study drug treatment (see Section 5.6) should be reported (see Sections 5.3.1 and 5.4.2 for instructions for reporting serious adverse events). Adverse events assessed by the investigator as related to study drug should be followed until the event resolves or the event is assessed as irreversible, chronic, or stable, even if patient's participation in the study has ended.
- bb Record all concurrent ocular procedures performed on the study or non-study eye.
- cc After each study treatment visit, the site must contact the patient 14 (±5) days after each treatment visit and query for adverse events; particularly any signs or symptoms of decreased visual acuity and/or inflammation (e.g., painful red eye, floaters, scotoma, pain); if the patient reports any concerning signs and/or symptoms, the patient must be evaluated by the investigator as soon as possible.

Appendix 2
Schedule of Activities: Q8W Arms

	PreBL	Baseline	D	ay					Weel	k Visit						
	Scrn a	Scm b	1	8	8	16	24	32	40	48	56	64	72	76 c		
Assessment Windows (Days)	–120 to –31	-30 to -1		±2	±5	±5	±5	±5	±5	±5	±5	±5	±5	±5	U∨	Early Term d
Written informed consent e	Х	х														
Review of inclusion and exclusion criteria	х	х	Х													
Medical and surgical history including tobacco history f		х														
Demographic information g		х														
Historical ocular image collection h			Х													
PreBL FAF and NI image collection i, j		х														
Randomization (IWRS) k			Х													
Physical examination		х													χI	Х
Vital signs m	Х	х	Х												χI	Х
Hematology, coagulation, lipids, serum chemistry (central laboratory) n		х						х					x		х¹	х
Urine pregnancy test º			X		х	х	х	х	х	X	X	Х			х¹	
Serum pregnancy sample p		х														
Whole blood sample for HtrA1 genotyping		х														
Plasma sample for biomarker			X							X			Х	х	χI	Х
Whole blood sample for biomarkers (clinical genotyping)			х													

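### Recording of new non-serious adverse events ends 28 days after each patient's own last dose, which conflicts with the later visits meant to monitor them and with the Week 76 rule for serious events

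*Combined protocol and SAP*

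**What the plan says.** **General window.** Section 5.3.1: "After initiation of study drug, all adverse events will be reported until 28 days after the final dose of study drug". Footnote aa of Appendix 1 agrees: "Adverse events will be recorded starting on Day 1 after the study treatment until 28 days after the final dose of study drug". The same footnote in Appendix 2 says the same.

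**After day 28.** Section 5.3.1 continues: "After the 28-day period, only serious adverse events (1) caused by a protocol-mandated intervention", or (2) thought to be related to earlier study drug. Section 5.6 repeats this limit and words it by when the event occurs.

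**Serious events and events of special interest.** Section 5.4.2.2 says that these "should be reported within 24 hours after learning of the event until the final study visit (Week 76"), without the restriction on cause.

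**Visits after the last dose.** Section 3.1 places an "early termination visit after a minimum of 30 days have elapsed following the final study treatment for monitoring of adverse events". The schedules mark adverse events at Weeks 72 and 76 and at early termination. Of patients who stop treatment, Section 4.6.1 says "they should be strongly encouraged to stay in the study and undergo as many scheduled visits as possible".

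**Week 76 sampling.** Both schedules include an aqueous humor sample at Week 76. Section 5.1.3 says of this sampling that "patients will be monitored closely for occurrence of any potential adverse event associated with the procedure". Section 3.1.1 adds an ocular-symptom call 7–10 days later for patients who do not enter the extension study.

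**The concern.** The window is tied to the patient's own last dose, not to the end of observation. Three consequences follow.

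- A visit whose stated purpose is adverse-event monitoring always takes place after the window for new non-serious events has closed. At Week 76, and at Week 72 on Q8W, a site is prompted for adverse events that the footnote tells it not to record.
- A patient who stops treatment and stays in follow-up, as the protocol asks, has no recording of new non-serious events from day 29 after the last dose. The length of adverse-event follow-up then depends on how long the drug was tolerated.
- A serious event on day 40 that is neither drug-related nor caused by a protocol procedure is reportable under 5.4.2.2 and not under 5.3.1 or 5.6. A non-serious event of special interest on that day meets the same conflict.

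The safety objective (Section 2.2) compares how often, how severely and when adverse events occur relative to sham. Section 5.1.1.1 reports recurrent non-serious vitritis in this trial, and Section 5.3.5.6 counts each recurrence as a separate event. New non-serious ocular events late in follow-up are therefore a realistic category.

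**Working it through.** **Inputs**

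- Last planned dose: Week 68 (Q4W), Week 64 (Q8W), Section 3.1.
- Number of treatments: 18 (Q4W), 9 (Q8W), Section 3.1.
- Last dose to Week 76: 8 weeks (Q4W), 12 weeks (Q8W), Section 3.3.4.
- Recording window: last dose + 28 days, Section 5.3.1.
- Visit window: ±5 days, Appendices 1 and 2.
- Early termination: at least 30 days after the last treatment, Section 3.1.

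**Reproducing the plan's own figures.** Q4W doses at Weeks 0, 4, …, 68 number 68/4 + 1 = 18, and 76 − 68 = 8 weeks. Q8W doses at Weeks 0, 8, …, 64 number 64/8 + 1 = 9, and 76 − 64 = 12 weeks. All four figures match.

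**Window for completers.** Window end = last dose + 4 weeks. Uncovered time = Week 76 − window end, out of 76 × 7 = 532 days.

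| Schedule | Window ends | Uncovered to Week 76 | Share |
|---|---|---|---|
| Q4W | 68 + 4 = Week 72 | 28 days | 28/532 = 5.3% |
| Q8W | 64 + 4 = Week 68 | 56 days | 56/532 = 10.5% |
| Pooled sham (1:1 mix) | (72 + 68)/2 = Week 70 | 42 days | 42/532 = 7.9% |

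The Q8W window is 4 weeks shorter than the Q4W window (68/72 = 0.944, or 5.6% shorter). Against pooled sham, Q4W active is 2.9% longer (72/70 = 1.029) and Q8W active is 2.9% shorter (68/70 = 0.971). Against sham on the same schedule, the planned difference is zero.

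**Where the visits fall, in days after the last planned dose.** The ranges allow ±5 days on both the dose and the visit.

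| Visit | Q4W | Q8W |
|---|---|---|
| Week 72 | 28 (18–38) | 56 (46–66) |
| Week 76 | 56 (46–66) | 84 (74–94) |
| Early termination | ≥ 30 | ≥ 30 |

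Early termination is at least 2 days past the cut-off. Q8W Week 72 and every Week 76 visit lie outside the window throughout these ranges. Q4W Week 72 lies on the boundary.

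**Patients who stop treatment but stay to Week 76.** Uncovered days = (76 − week of last dose) × 7 − 28. The stopping weeks are illustrative assumptions; the documents give no distribution.

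- Last dose Week 12: 64 × 7 − 28 = 420 days (420/532 = 79%)
- Last dose Week 24: 52 × 7 − 28 = 336 days (336/532 = 63%)
- Last dose Week 48: 28 × 7 − 28 = 168 days (168/532 = 32%)

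**Week 76 sampling.** Aqueous humor is taken on Day 1 and at Weeks 4, 24, 48 and 76 (Q4W), or on Day 1 and at Weeks 8, 24, 48 and 76 (Q8W). For completers, one of the five procedures falls outside the window in every arm.

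**The case against.** **The rules can be partly reconciled.** Section 5.6 speaks of when an event occurs. On that reading, an event that starts by day 28 and is found on day 30 or later is still recordable, and a visit after day 30 can close out a complete 28-day window. This stands: the timing of the early-termination visit alone does not show that events found there are lost. But 5.3.1 does not say whether onset or discovery governs, and events with onset after day 28 remain excluded.

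**Section 5.3.1 also asks about adverse events at every contact.** Its opening paragraph has investigators enter all of them on the case report form, so some sites may record them anyway. That makes the text ambiguous; the explicit 28-day limit still follows in the same section and in footnote aa.

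**The ocular findings are still collected.** This stands. Visual acuity, pressure, slit lamp and ophthalmoscopy continue at Weeks 72 and 76 and at early termination, and SD-OCT at Week 72 and early termination. Concomitant medications and ocular procedures are recorded to Week 76. Section 6.5 summarises ocular assessments and imaging apart from adverse events, and neovascular AMD is counted over the whole study. Sight-threatening events are serious by rule. What these data lack is the adverse-event entry with severity, causality and dates, as well as non-ocular events and symptoms between visits.

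**A reader might infer that the rule undercounts harm from the drug.** The documents do not establish this. Each active arm has the same planned window as sham on its own schedule. More stopping on drug because of inflammation is plausible, but no stopping rates by arm are given, and the vitritis cases in Section 5.1.1.1 led to leaving the study, not to staying on untreated.

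**A reader might also infer that 28 days is too short** because Section 3.3.1 cites biomarker data "which suggest inhibition of HtrA1 activity through at least 8 weeks following a 20-mg dose". That is a pharmacodynamic result. Section 5.1.1.1 attributes the inflammation seen in animals to an immune response and calls the mechanism in this trial not fully understood, so the duration of inhibition does not set the adverse-event window.

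**Conclusion.** The conflict is real and needs correcting. Recording of new non-serious adverse events ends nominally at Week 72 for Q4W completers, at Week 68 for Q8W completers, and earlier for patients who stop treatment and stay in follow-up. The visits and prompts run on to Week 76 or early termination. The rules for serious events and events of special interest after day 28 also contradict each other.

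The loss is limited to the adverse-event record of non-serious events with onset after day 28. The planned imbalance is 4 weeks between Q4W and Q8W, or about 2 weeks either way from the pooled-sham average. The Week 76 procedure is uncovered in all arms alike and creates no imbalance. Any bias in the comparison with sham beyond the 2 weeks requires different stopping rates by arm; its size is unknown, and its direction is plausible but not shown.

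This rests on three assumptions: visits at their nominal dates, a final dose that for sham patients means the final sham treatment, and sites that follow the 28-day limit as written.

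**What to change.** Reconcile Sections 5.3.1, 5.4.2.2 and 5.6 with footnote aa of both appendices:

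- Record all adverse events, serious or not, to Week 76 or the early-termination visit for every patient, whatever the date of the last dose.
- State that onset date governs whether an event falls within a period.
- For patients not entering the extension study, include events after the Week 76 aqueous sampling that are reported at the existing 7–10 day call.
- In the safety analyses (Section 6.5), make the summary to Week 76 the main table, and give a last-dose-plus-28-days table as supportive.

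For completers, the schedule-driven gap before Week 76 then falls from 28 or 56 days to 0 in all arms. Early stoppers who stay in follow-up are recorded for as long as they attend. The visits and adverse-event prompts already exist, so the cost is amendment wording and one extra table. The drawback is that some late, disease-related events will be counted in all arms; the supportive table shows how much they matter.

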## 3.1.1 Open-Label Extension Study and Study Follow-Up

After completing the study's last visit (Week 76), eligible patients will have the option to enroll in an open-label extension study (GR42558) of GAllego and receive open-label FHTR2163 injections. The Week 76 visit will serve as the final visit for the GAllego study (GR40973) and the first (Day 1) visit for Study GR42558. Dosing frequency will remain consistent with each patient's dosing schedule in this study (i.e., Q4W or Q8W).

Patients who do not enter Study GR42558 will be contacted 7–10 days after the last visit by a follow-up call to elicit reports of any decrease in vision, eye pain, unusual redness, or other new ocular symptoms in the study eye.

## 3.1.2 Internal Monitoring Committee

An IMC will monitor safety and study conduct on an ongoing basis. Members of the IMC will be unmasked to treatment allocation and will include Sponsor representatives from multiple functions who are not involved in the conduct of the study. The IMC may request that additional Sponsor scientists or other external scientists participate in the data analyses and review. The IMC members will not have direct contact with investigational staff or site monitors. Further details regarding roles and responsibilities are outlined in the IMC Agreement.

### 3.2 END OF STUDY AND LENGTH OF STUDY

The end of the study is defined as the date when the last patient, last visit (LPLV) occurs. LPLV is expected to occur approximately 76 weeks after the last patient is randomized to the study. In addition, the Sponsor may decide to terminate the study at any time.

### 3.3 RATIONALE FOR STUDY DESIGN

The primary efficacy objective of this Phase II study is an anatomic endpoint, specifically, the growth rate of GA lesion area based on FAF imaging (Biarnes et al. 2015). The anatomic primary endpoint provides a more sensitive, quantitative, and earlier metric of GA progression and serves as a surrogate for vision loss. The 76-week study length was designed because of the slow progressing nature of the disease and to maximize the opportunity to ascertain a treatment effect (Fleckenstein et al. 2018).

## 3.3.1 Rationale for FHTR2163 Dose and Schedule

To provide assessment of the relationship between dosing interval and efficacy, two FHTR2163 treatment arms will be evaluated in this Phase II study, a 20-mg dose administered ITV Q4W and a 20-mg dose administered ITV Q8W.

In the Phase I study (GR39821), 20 mg of FHTR2163 was the maximum dose tested and was administered ITV Q4W for three doses. The 20-mg dose and the Q4W interval were found to be well tolerated. The 20-mg dose administered Q4W allows evaluation of the highest exposure of FHTR2163.

The Q8W dosing regimen will be assessed to allow evaluation of a longer dosing interval, which is a major priority for patients, caregiver, and physicians in this disease indication. On the basis of the observed serum and aqueous PK data, estimated vitreal drug concentrations for a typical patient treated with 20 mg Q8W are maintained above the 50% inhibitory concentration of 3.58 nM established in a cynomolgus monkey PK/pharmacodynamic (PD) study (16-0265). In addition, the Q8W dosing interval is supported by the observed PD biomarker data from aqueous humor samples collected during the Phase I study (GR39821), which suggest inhibition of HtrA1 activity through at least 8 weeks following a 20-mg dose.

## 3.3.2 Rationale for Patient Population and Analysis Groups

Currently, there are no approved treatments to reverse, prevent, or reduce the progression of GA secondary to AMD and the associated decrease in visual function. Consequently, a significant unmet need exists for treatment of this serious condition.

This study will enroll a target population of patients with a diagnosis of GA secondary to AMD. Key eligibility criteria were selected to enrich the study population for patients with GA who may have more rapid growth of GA lesions to maximize the chances of detecting progression of disease and treatment effects over the planned study duration as well as to identify patients most likely to potentially benefit from the treatment. The key eligibility criteria and rationale for the criteria are presented below.

## Evidence of Geographic Atrophy in Study Eye and Non-Study (Fellow) Eye

Bilateral GA represents the majority of the population (approximately 60%–67%) diagnosed with GA as reported in two natural history studies (Holz et al. 2007; Sunness et al. 2007) and has been associated with an increased rate of GA lesion growth compared with unilateral GA (Sunness et al. 2007).

## Presence of Hyperautofluorescence Adjacent to the GA Area in the Study Eye (i.e., Banded or Diffuse Junctional Fundus Autofluorescence Patterns)

Holz et al. (2007) described four major perilesional FAF patterns (none, focal, banded, and diffuse) that were correlated with the rate of GA lesion growth in the longitudinal natural history arm of patients with GA secondary to AMD in the multicenter FAM study.

Holz reported that GA lesions with banded or diffuse junctional patterns expanded at a significantly higher rate than lesions with focal or no hyperautofluorescence. Of note, approximately 70% of the patients in the FAM study exhibited the banded or diffuse junctional perilesional FAF patterns. Furthermore, the diffuse-trickling pattern of FAF will be excluded due to a much faster progression rate relative to the other forms as well as the potential for being a distinct form of GA (Holz et al. 2007; Fleckenstein et al. 2014).

